EXERT is a multisite, randomized, single-blind trial comparing the effects of supervised moderate/high intensity aerobic exercise (70-80% Heart Rate Reserve [HRR]) versus stretching/balance (<35% HRR) in 296 adults with amnesic mild cognitive impairment (MCI).

3. Randomization

We use a randomized, single-blind study design where randomization is undertaken using a simple 1:1 schedule to either the aerobic exercise (AX) or stretching, balance and range of motion (SBR) group, and stratified by site, ApoE4 carrier status (yes or no), and sex. After 12 months of supervised exercise, participants transition to independent exercise (without supervision) and are instructed to continue their assigned exercise regimen for an additional 6 months to test the efficacy of a translational model.

4. Power and Sample Size Determination

Power calculations were based on two-sample t-tests. Sample sizes were estimated using 12-month ADAS-Cog change scores from the ADCS MCI trial, targeting power=80%, 2-sided alpha=5%, and SD=4.1. Calculations ranged over effect sizes in ADAS-Cog from 1.0–2.0, and dropout rates from between 10-25%, which are similar to other reports, including multi-center trials of physical activity interventions in older cohorts. The trial was powered to conservatively accommodate 20% attrition. Based on these considerations, and an effect size of 1.5, 291 total subjects were required. We enrolled 296 participants into the trial. The primary outcome measure is a validated composite score (ADAS-Cog-Exec)¹ derived using an optimally weighted combination of select subtest scores from the Alzheimer's Disease Assessment Scale – Cognitive Subscale, version 13 (ADAS-Cog13), supplemented with tests of executive function (Trail Making Test, Digit Symbol Substitution Test, Word Fluency), and select box scores of the Clinical Dementia Rating (CDR) scale (Memory, Orientation, Judgement and Problem-Solving). This approach that includes composite measures is expected to increase statistical power. In light of evidence showing exercise benefits on executive function, the addition of the Trail Making Test, Digit Symbol Substitution (DSST), Word Fluency, and CDR subscale scores to the ADAS-Cog-Exec composite should also increase sensitivity and power.

5. Study Aims

5.1 Primary Aim

To test the hypothesis that 12 months of supervised moderate/high intensity aerobic exercise, relative to a stretching/balance/range of motion control, improves cognitive function measured using the ADAS-Cog-Exec, in older adults with amnesic MCI.

5.2 Secondary Aims

- 5.2.1 Key second aim:** to test the hypothesis that 12 months of aerobic exercise, relative to the control, improves scores on the primary outcome (ADAS-Cog-Exec) in the subset of participants who had the opportunity to complete a full 12 months of the study (i.e., 12 months of exercise and the 12 Month outcomes assessment) before the COVID-19 pandemic affected trial conduct.
- 5.2.2** To test whether 12 months of supervised aerobic exercise, relative to the control, improves executive function and episodic memory measured by domain-specific composite scores.
- 5.2.3** To test whether 12 months of aerobic exercise, relative to the control, reduces brain atrophy and increases blood flow in the hippocampus and in prefrontal (superior frontal, caudal-middle frontal, rostral-middle frontal, pars opercularis, pars triangularis) and AD signature (parahippocampus, fusiform, inferior temporal, middle temporal, inferior-parietal) composite regions, measured using volumetric and arterial spin labeling magnetic resonance imaging (MRI).
- 5.2.4** To test whether 12 months of aerobic exercise, relative to the control, favorably alters AD biomarkers in CSF (ab42/ab40, ab42/tau, ab42/p-tau) and blood (ab42/ab40).

5.3 Exploratory Aims

- 5.3.1** To examine intervention effects on secondary outcomes listed above (**Section 5.2.2-5.2.4**) in participants who had the opportunity to complete a full 12 months of the study before the pandemic affected trial conduct.
- 5.3.2** To test whether 12 months of aerobic exercise, relative to the control, favorably affects MRI whole brain, ventricular and entorhinal volumes; perfusion in whole brain, gray matter and white matter; and individual AD biomarkers in CSF (ab42, ab40, total tau, p-tau, BDNF) and blood (ab42, ab40).
- 5.3.3** To test whether 12 months of aerobic exercise, relative to the control, reduces clinical ratings of cognitive impairment as measured by the CDR – Sum of Boxes, and total score on the ADAS-Cog13.
- 5.3.4** To test whether 12 months of aerobic exercise, relative to the control, improves self-report measures of cognitive function and well-being, including (1) daily living skills (ADCS–Activities of Daily Living–MCI); (2) BRIEF-A: Behavior Rating Inventory of Executive Function–Adult Version); (3) mood (GDS); (4) health-related quality of life (NPI: Neuropsychiatric Inventory; SF-36: 36-Item Short Form Health Survey; EuroQol: 5-Item Health Questionnaire); (5) subjective memory concerns (CCI: Cognitive Change Index); and (6) Study Partner Self-Assessment Questionnaire.
- 5.3.5** To examine enduring cognitive effects (measured by ADAS-Cog-Exec, Executive Function and Episodic Memory Composites) of the intervention following a 6-month extension (through Month 18) when the prescribed

exercise is continued without supervision.

- 5.3.6** To explore whether sex, age, baseline AD biomarker profile in CSF (ab42/ab40, ab42/tau, ab42/p-tau) and blood (ab42/ab40), and ApoE4 genotype (e4+, e4-) predict treatment response.

6. Populations of Interest

6.1 Modified Intent-to-Treat (mITT) Population: Includes all eligible participants who (1) began the exercise intervention (Intervention Session 1) and (2) completed at least one post-baseline assessment for the primary analysis at Month 6 or Month 12. All consented randomized participants are grouped according to the treatment assigned at randomization, regardless of any protocol violations.

6.1.1 mITT Pre-Pandemic Subset: Subset of mITT participants who had the opportunity to complete a full 12 months of the study prior to the pandemic-related study pause on March 23, 2020. Individuals are included in this subset if they (1) completed the Month 12 primary outcomes assessment before the study pause, (2) completed an early termination visit before the study pause, or (3) withdrew consent, were lost to follow-up, or died before the study pause.

6.1.2 mITT Pandemic Subset: mITT participants who did not have the opportunity to complete a full 12 months of the study prior to the pandemic-related study pause on March 23, 2020. Individuals are included in this subset if they are not a member of the Pre-Pandemic Subset.

6.2 Per-Protocol (PP) Population: Includes all eligible participants meeting all three of the following criteria: (1) completed the 12-month assessment for the primary analysis, (2) attended at least 70% of the supervised exercise sessions, and (3) completed a mean total supervised exercise time of at least 40 minutes.

6.3 Intent-to-treat (ITT) Population: Includes all eligible and randomized individuals.

6.4 Safety Population: Includes all randomized participants who participated in at least one exercise session (Intervention Session 1).

7. Analyses Populations: Definitions

7.1 Clinical Outcome Analyses: The primary, secondary, and exploratory clinical outcome analyses will be conducted in the mITT Population, the mITT Pre-Pandemic Subset, the mITT Pandemic Subset, the ITT Population, and the Per-Protocol Population.

7.2 Safety Analyses: The primary safety analyses will include the Safety Population.

8. Enrollment and Participant Flow

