## 9.5 Month 12 (Visit 4) / or Early Termination

The Month 12 assessment will provide the primary endpoints to evaluate trial efficacy, and should be completed 12 months (+/- 2 weeks) from the participant's first appointment at the YMCA that initiated the intervention. The following procedures may be completed over multiple days, but within a 7-day window. Participants will be instructed to bring their HR monitor to the appointment and to refrain from exercise for 24 hours prior to cognitive testing, fMRI (for approved sites), and the LP. Cognitive testing should not be completed while participants are fasting, and if conducted after an LP, testing must be administered at least 48 hours following the procedure. Month 12 procedures include:

- Fasting blood collection for clinical labs
- Fasting blood collection for banking
- Medication review
- Brief physical exam, vital signs, weight
- Brief neurological exam
- AE query
- Briefly review adherence with participant using report provided through EDC and entries in the Physical Activity Logs (adherence will be regularly monitored by the YMCA Trainer, the Y-PM and the Intervention Oversight Team as well)
- Cognitive assessment
  - Primary outcomes assessment (administer the following tests before administering other cognitive/behavioral instruments)
    - ✓ ADAS-Cog13
    - ✓ Trail-Making Test
    - ✓ DSST
    - ✓ Category and Letter Word Fluency

- Secondary outcomes assessment
  - ✓ 3MSE/MMSE
  - ✓ iPad computer tests
    - Cogstate: DET, IDN, OCL, OBK, GMLT, FNAME, BPSO
    - NIH Toolbox: Flanker, DCCS
- Behavioral/functional and other outcomes assessments
  - Staff-administered questionnaires
    - ✓ CDR
    - ✓ ADCS-ADL-MCI
    - ✓ BRIEF-A
    - ✓ NPI
  - Self-administered questionnaires
    - ✓ By participant
      - Cognitive Change Index
      - SF-36
      - EQ5D
      - Research Satisfaction Survey
    - ✓ By study partner
      - Study Partner Self-Assessment Questionnaire (SF-36, Pittsburgh Sleep Quality Index, Insomnia Severity Index)
      - EQ5D (as it relates to participant)
- 400 m Walk Test
- Brain MRI
  - At approved sites, protocol will include fMRI sequences
- LP
  - CSF may be collected at this visit, even if not successfully collected at Baseline
  - Follow-up telephone call by staff within 24 hours to query AEs
- Dispense ActiGraph Link for actigraphy data collection
  - Place on the participant's non-dominant wrist to initiate recording period

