- 12.2** Intervention effects on a supplemented ADAS-Cog-Exec that includes Letter Fluency (mean of F and L Fluency) will be examined in the mITT Population, the Pre-Pandemic Subset, and the Pandemic Subset using a similar approach described for Aim 1.
- 12.3** Intervention effects on the primary and key secondary outcomes will be examined in the Pandemic Subset using the approach described for Aim 1.
- 12.4** Subgroup analyses testing whether the following variables predict cognitive, vMRI, ASL MRI, and specimen biomarker response to the intervention in the mITT

Population and Pre-Pandemic Subset: sex, age, APOE genotype, baseline biomarker status (CSF: ab42/ab40, ab42/tau, ab42/p-tau; and blood: ab42/ab40).

12.5 In the Pandemic Subset, test whether pandemic-time-in-study altered intervention response on primary and key secondary outcomes. Pandemic-time-in-study coding is provided below.

- **Code 1:** At the time of study pause, participant had completed the Month 6 outcomes assessment (but not the Month 12 outcomes assessment)
- **Code 2:** At the time of study pause, participant was due for Month 6 or Month 12 outcomes assessment but did not complete until after the pause following a brief (6-8 weeks) ramp-up to prescribed intervention intensity.
- **Code 3:** At the time of study pause, participant had not yet completed an outcomes assessment.

13 Analyses of Executive Function and Episodic Memory Composites

Individual test scores included in each composite are listed below. Test scores are converted to z-scores and then averaged to create the composite score. Z-scores for longitudinal change are calculated by subtracting each participant's baseline score from the follow-up score (Month 6, Month 12) to obtain a change score, then dividing each change score by the baseline standard deviation for that measure. Composite scores are computed when 50% or more of the component test scores are available.

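### SAP 6.1.1 defines the Pre-Pandemic Subset by opportunity to complete 12 months, yet late starters enter it only by leaving before the pause (small expected effect)

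*SAP*

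**What the plan says.** The key second aim (SAP 5.2.1) concerns participants with the opportunity for a full 12 months in the study, spelled out as "i.e., 12 months of exercise and the 12 Month outcomes assessment) before the COVID-19 pandemic affected trial conduct". SAP 6.1.1 opens in the same way: "Subset of mITT participants who had the opportunity to complete a full 12 months of the study prior to the pandemic-related study pause".

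The inclusion rule that follows has three alternatives joined by *or*. The first is a Month 12 primary outcomes assessment completed before the pause. The other two are "2) completed an early termination visit before the study pause, or (3) withdrew consent, were lost to follow-up, or died before the study pause". The Pandemic Subset (SAP 6.1.2) is the complement: "Individuals are included in this subset if they are not a member of the Pre-Pandemic Subset". Both subsets sit inside the mITT population, whose members must have "completed at least one post-baseline assessment for the primary analysis at Month 6 or Month 12" (SAP 6.1).

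Protocol 9.5 times the Month 12 visit, which "should be completed 12 months (+/- 2 weeks) from the participant's first appointment at the YMCA that initiated the intervention". SAP 12.5 codes members of the Pandemic Subset by their position at the pause. Code 1 reads "At the time of study pause, participant had completed the Month 6 outcomes assessment (but not the Month 12 outcomes assessment".

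**The concern.** Opportunity is fixed by the start date. Leaving is not. Criterion (1) implies an early enough start; criteria (2) and (3) require only that the person had gone by 23 March 2020. I found no start-date or randomisation-date condition in SAP 6.1.1, 6.1.2, 7, 8.2 or 11.2.1.

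Among late starters, the key secondary population therefore takes in the leavers and none of the continuers. The Pandemic Subset has the mirror problem, since it holds only people still in the study at the pause. The Pre-Pandemic Subset is used again in the exploratory analyses (11.3) and in 12.2 and 12.4. If the safety summaries in 15.1 use the same definition, a late starter is counted there after leaving or dying but not after continuing.

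There is also a data question. SAP 9 counts people who only stop treatment as early terminations, and Protocol 10.0 encourages them to attend all later scheduled visits. SAP 6.1.1 sets no data cut-off, so someone with an early termination visit before the pause and a Month 12 assessment after it is Pre-Pandemic with a pandemic-era score. SAP 8.2 labels people with a post-pause Month 12 assessment as Pandemic, so the two sections disagree about this person.

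**Working it through.** **Plan's own figure.** The SAP gives no size for either subset. Its trial-level inputs (SD 4.1, effect 1.5, 80% power, two-sided 5%) give 2 × (1.960 + 0.842)² × 4.1² / 1.5² = 117.3, so 118 per arm and 236 in total. Dividing by 0.80 for attrition gives 295, close to the stated 291. The point does not depend on this.

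**Cut-off date.** In calendar months, a start on 5 April 2019 plus 12 months minus 14 days gives 22 March 2020, and a start on 6 April gives 23 March. So 5 April is the last start that allows an in-window visit before the pause. If the 4-week month that Protocol 6.3 uses for its phases applied, 5 May 2019 + 336 − 14 days = 22 March 2020.

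**Two people side by side.** Both start on 1 July 2019 and attend Month 6 in January 2020. One withdraws in February 2020 and is Pre-Pandemic by criterion (3). The other keeps exercising and is Pandemic, Code 1. Their opportunity was identical.

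**Size.** The documents give no accrual dates and no dropout by arm, so the following is assumed: 296 randomised; a share L of 25-50% starting evenly over the 366 days before the pause; dropout q = 20%, even over 366 days; late window 6 April 2019 to 22 March 2020 = 352 days; Month 6 at 183 days.

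- Month 6 visit required, late leavers admitted: 296 × L × q × [(352 − 183)²/2] / 366² = 1.6 (L = 0.25) to 3.2 (L = 0.50).
- Every late leaver has a usable early termination visit (upper bound): 296 × L × q × (352²/2) / 366² = 6.8 to 13.7.
- Starters on or before the cut-off: 296 × (1 − L × 352/366) = 225 to 154.

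| | Month 6 required | Upper bound |
|---|---|---|
| Late leavers as share of subset | 0.8% to 2.2% | 3.0% to 8.2% |
| Non-completers with a start-date clause | 11.1% | 20.0% |
| Non-completers as written | 11.8% to 13.1% | 22.4% to 26.5% |

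By contrast, 29 to 58 late starters with a Month 6 visit were still exercising and go to the Pandemic Subset.

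**Shift in the treatment contrast.** If leavers score d points worse in both arms, the shift is d times the between-arm difference in how far the rule raises the non-completer share. With 20% dropout in both arms it is zero. With an assumed 25% versus 15%, the multiplier is 0.0033 to 0.0094 (Month 6 required) or 0.0085 to 0.0219 (upper bound). For d = 2 that gives 0.007 to 0.019 or 0.017 to 0.044 points; for d = 4.1 (1 SD), 0.014 to 0.038 or 0.035 to 0.090. A simulation with d = 2 gave 0.006 and 0.020, and 0.016 and 0.043.

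Equal dropout does not by itself guarantee zero. If 20% leave in each arm but the leavers' deficit differs between arms by 2 points, the shift is 2 × the rise in non-completer share: 2 × 0.0069 to 2 × 0.0198 = 0.014 to 0.040 (Month 6 required), or 2 × 0.0236 to 2 × 0.0654 = 0.047 to 0.131 (upper bound). A separate simulation had 25% versus 15% dropout, with leaving related to outcome only in the aerobic arm. It gave shifts of 0.003 to 0.047 SD. The largest, 0.047 × 4.1 = 0.19 points, needs 120 late starters and early termination visits that count. The standard error of the subset contrast was about 0.125 to 0.16 SD, or 0.5 to 0.65 points at SD 4.1.

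**The case against.** *The opening sentence already limits the subset.* It can be read that way, but nothing makes it operational, and a programmer will follow the inclusion list. Two programmers could build different key secondary populations. If the limit was intended, the clause only writes it down.

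*Leavers were untouched by the pandemic, so sorting by exposure is reasonable.* This is a fair alternative concept, but not the stated one, which is the chance of a full 12 months. It also fails for the early terminator who returns for Month 12 after the pause.

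*The mITT filter and the reporting limit the damage.* This largely stands. A late leaver needs a qualifying assessment. The flow diagram in 8.2 shows discontinuations by subset and by arm, and SAP 9 compares premature discontinuation between arms with Fisher's exact test. None of this is split by start date, so a reader could see unequal dropout but could not undo the selection. The upper-bound count is generous: people who withdrew, were lost or died may have no early termination visit, and the telephone procedures listed in Protocol 10.0 include the CDR but not the ADAS-Cog13, Trails, DSST or fluency.

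*A stronger reading.* A reader might infer that the key secondary result is biased, perhaps against aerobic exercise, because Protocol 4.2 links high intensity to lower adherence. The documents do not support that. Adherence is not dropout, no dropout rate by arm is given, and the earlier trials cited report retention above 80% (Protocol 6.3.1) and comparable serious adverse event rates across groups (Protocol 2.2). Nor does the text support a claim of widespread pandemic-era data: the consent-withdrawal example contributes only its Month 6 score.

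**Conclusion.** The rule as written does not match the definition that it is meant to apply, and for late starters it selects on a post-randomisation event. That follows from the text without any assumption. The size does rest on assumptions. With 25-50% of starts in the last year before the pause and 20% dropout, about 2-3 people are misplaced on SAP 6.1's wording, with an upper bound of about 7-14. Bias arises only if dropout or the leavers' deficit differs between arms. In the scenarios tried, the shift was below the sampling error of the contrast. The point shifts and the 1.5-point benchmark are on the ADAS-Cog scale and are only indicative for the weighted ADAS-Cog-Exec composite. The primary mITT analysis is unaffected. This is a minor point, worth correcting because the population carries the key second aim.

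**What to change.** - Keep criterion (1). Add to criteria (2) and (3): *had Intervention Session 1 on or before [cut-off]*. State one date consistent with the Month 12 window: 5 April 2019 in calendar months, or 5 May 2019 if the 4-week month applies.
- In Pre-Pandemic Subset analyses through Month 12, use only assessments made before the pause. Analysis 11.3.5 runs to Month 18 and needs its own stated rule, because the same cut-off would drop Month 18 visits of people who qualify under criterion (1).
- State whether an early termination visit counts as a post-baseline assessment for mITT.
- Late starters who left before the pause then fall into the Pandemic Subset. Flag them in 11.3.5, 12.2, 12.3 and 12.5, and exclude them from the 12.5 coding: Code 1 or Code 3 would fit by wording, though they had no pandemic time in the intervention.
- Continuers who were due for an assessment and "participant was due for Month 6 or Month 12 outcomes assessment but did not complete until after the pause" stay Pandemic.
- Reconcile the label in 8.2, and report the number reclassified by arm.
- Run a pure start-date definition of both subsets as a sensitivity analysis.

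The cost is SAP wording; first-session dates are already needed to schedule visits. The Pre-Pandemic Subset becomes slightly smaller. Some selection at the boundary remains because criterion (1) is kept. Starts from 9 March to 5 April 2019, whose visit window straddles the pause, would number 296 × L × 28/366 = about 6-11 people under the same assumptions. In simulation, about 2-5 continuing starters on or before the cut-off were still unassessed at the pause and would stay Pandemic.

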8.1 Accrual of the Study

Tables will summarize accrual by study site, and figures will summarize the overall rate of accrual over calendar time. The observed rate and projected rate of accrual will be displayed in a graph (the projected rate assumes uniform accrual over time).

8.2 Study Flow CONSORT Diagram

A description of participant flow per the CONSORT guidelines² and checklist will be provided. The diagram will describe study status from screening to the end of the study. At each stage, reasons for persons not moving forward will be summarized by frequency and category. The diagram will include the following information:

- Number and reasons for those who screen failed
- Number of participants randomized
- Number of participants who completed the Month 12 assessments
- Number of participants who completed the Month 12 assessments before the study pause (Pre-Pandemic Subset) and after the study pause (Pandemic Subset)
- Number and reasons for participants who discontinued study before the Month 12 assessments for the entire cohort, and for the Pre-Pandemic and Pandemic Subsets

The CONSORT diagram is separated by study arm after the randomization step.

9. Early Termination

Early termination from the study includes participants who leave the study and/or discontinue treatment prior to completing the Month 12 assessments. Proportions of participants who prematurely discontinue the study prior to the Month 12 assessments will be compared between the study arms using Fisher's exact test.

10. Evaluation of Demographics and Baseline Characteristics

Tables will summarize the mITT Population, the mITT Pre-Pandemic Subset, and the mITT Pandemic Subset at baseline, and by study arm. Tables will also summarize the ITT and Per-Protocol Populations. Descriptive statistics will be presented as N, mean, standard deviation, minimum, 25th quartile, median 75th quartile and maximum for continuous variables and frequency tables (row, column percentages) for categorical variables. Statistical comparisons will be performed between randomized arms using Wilcoxon Rank Sum Test (for continuous variables) or Fisher's exact test (for categorical variables).

- Baseline Demographics: All variables collected in the Participant Demographics form
- Baseline Medical History: All variables collected in the Medical History Form
- Baseline Vital Signs: All variables collected in the Orthostatic Vital Signs Form
- Baseline Clinical Measures

11. Analyses of Study Outcomes

